10.6 Concomitant Therapy

Concomitant medication will be allowed, with the exception of the prohibited medications noted below, or unless deemed otherwise by the Principal Investigator/Sub-Investigator.

The following concomitant medications are prohibited from the signing of informed consent until the TOC/EOS Visit on Study Day 5:

- any drug such as aspirin or ibuprofen (Advil) which can cause GI bleeding
- any medication considered "traditional" by the Investigator and that has an influence of GI function
- antimicrobial agents with an expected activity against enteric bacterial pathogens (e.g., trimethoprim/sulfamethoxazole, quinolones, azithromycin)
- oral antibiotic medications
- antimuscarinic drugs (e.g., Tolterodine, Solifenacin, Darifenacin, Trospium chloride), Oxybutynin. A complete list of commonly used medications with antimuscarinic effects is provided in Appendix II.

- drugs effecting GI motility such as antimotility agents, adsorbent agents, prokinetic agents and other stimulants of GI contractility, laxatives and cathartics, antacids, or anti-diarrheal agents
- analgesic drugs (opioids or non-steroidal anti-inflammatory drugs)
NOTE: Use of paracetamol is allowed for a maximum of 2 consecutive days
- fiber products
- probiotics
- herbal products/dietary supplements with effect on the GI system (i.e., Rue [rude], wormwood, estafiate, Espazote de zorrillo, chamomile [manzanilla]).

The administration of any concomitant medication or herbal/dietary supplements during the study (from signing of informed consent until the TOC/EOS Visit) will be recorded by patients on the Supplemental Form provided at the Screening/Randomization Visit. The start and stop date should be recorded along with the reason for the medication use.

10.7 Complaints Connected to Study Drugs

10.7.1 Definitions

Quality complaints are complaints connected to the investigation's medicinal product (test product, reference product or placebo) and include:

- technical complaints are complaints connected to the quality of the products and include the following cases:
 - any fault of quality and/or effectiveness, e.g., change of visual appearance, change of amount, damaged tablets, presence of foreign matter
 - any fault of the labeling, e.g., missing or illegible label
 - any falsification of the medicinal product, e.g., suspected product mix-up, tampering or counterfeiting.
- transport complaints are complaints connected to the transport of the product, such as damaged transport carton, damaged packaging upon receipt of the shipment, missing drugs from the shipment package, unsuitable transport conditions.

10.7.2 Process

In case any of the above quality complaints are detected or received the completed Quality Complaint Report form must be sent to the Sponsor (study manager) within 24 hours. In parallel the local monitor or Clinical Research Associate of the respective study must be informed about the complaint. If possible, a photo of the affected material should be attached to the report. Affected material should be retained and stored according to the storage conditions label and/or returned to Sponsor if requested by the Sponsor.

11 ASSESSMENT OF EFFICACY

11.1 Efficacy Endpoints

11.1.1 Primary efficacy endpoint

The primary endpoint is clinical cure at the TOC/EOS Visit (Study Day 5 \pm 1 day). Clinical cure is defined as either:

- no stools or only formed stools within a 48 hour period and no fever, with or without other enteric symptoms, OR
- no watery stools or no more than two soft stools passed within a 24 hour period with no fever and no other enteric symptoms except for mild excess gas/flatulence.

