9.3.2 Exclusion Criteria

Patients meeting any of the following criteria must not be enrolled in the study:

1. Hypersensitivity to rifaximin or any of the rifamycin antimicrobial agents or to any of the excipients of the study drug
2. Pregnant, breast feeding, or planning a pregnancy
3. Acute diarrhea for > 72 hours immediately prior to Randomization
4. Presence of:
 - a. fever (≥ 100 °F/37.8 °C), or
 - b. hematochezia (blood in stool; noted visually), or
 - c. clinical findings suggesting moderate or severe dehydration
5. Active, uncontrolled, or clinically significant diseases or disorders of the heart, lung, kidney, GI tract (other than infectious diarrhea in travelers), or central nervous system which would, in the judgment of the Investigator, compromise the patient's safety or successful participation in the clinical study
6. Administration of any of the following:
 - a. any antimicrobial agents with an expected activity against enteric bacterial pathogens (e.g., trimethoprim/sulfamethoxazole, quinolones, azithromycin) within 7 days preceding randomization
 - b. more than 2 doses of a symptomatic antidiarrheal compound such as antimotility agents, absorbent agents, and antisecretory agents within 8 hours preceding randomization
7. Use of any drug such as aspirin or ibuprofen (Advil), which can cause GI bleeding
NOTE: Acetaminophen (Tylenol) or paracetamol is acceptable for a maximum of 2 consecutive days.
If required, antimalarial prophylactic treatment, including doxycycline, is permitted prior to and during the study
8. Presence of a medical condition with regular GI symptoms (e.g. Crohn's disease, ulcerative colitis, indeterminate colitis, previous bowel surgery which impacts absorption long term, thyrotoxicosis, short bowel syndrome, etc.)
9. Patient requires medication which alters GI function (e.g., prokinetic agents and other stimulants of GI contractility, laxatives and cathartics, antacids, or anti-diarrheal agents)
10. Patient requires use of long term antibiotics (e.g. urinary tract infection prophylaxis, acne, etc.)
11. Previous enrolment in trials involving rifaximin, previous enrolment in this study or participation in any other drug investigational trial prior to enrolment, within previous 6 months
12. Active alcohol/drug dependence or abuse (excluding tobacco abuse), as determined by the Investigator

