13.2.2 Analysis Populations

The following analysis populations will be defined for the statistical analyses:

- The Safety population will include all randomized patients who received at least 1 dose of the study product.
- The mITT population will include all randomized patients who met all inclusion/exclusion criteria, received at least 1 dose of the study drug and recorded the number of formed and unformed bowel movements during Study Day 1.
- The PP population will include all randomized patients from the mITT population who do not have a major protocol deviation that would affect treatment evaluation. Patients who discontinue the study due to lack of treatment effect after completing 3 days of treatment or whose condition worsens and who require alternate or supplemental therapy for the treatment of TD should be included in the PP population (see Section 13.2.5 for the handling of missing values).

Major protocol deviations include but are not limited to:

- lack of compliance defined as having administered <75% or >125% of the scheduled doses for the specified duration of the study
- completion of the TOC/EOS Visit outside the specified visit window (Study Day 5 \pm 1 day) (if patient did not discontinue the study due to lack of treatment effect or worsening of the underlying condition requiring alternate or supplemental therapy).

Further major protocol deviations will be defined in the SAP.

The PP population will be the primary population for establishing equivalence of rifaximin and Xifaxan regarding the primary efficacy endpoint (clinical cure). The mITT population will be the primary population for evaluation of the study sensitivity comparing the proportions of clinical cure between rifaximin and placebo and Xifaxan and placebo.

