8.3 Protocol deviations

A listing will include the inclusion/exclusion criteria violated at Screening/Randomization as well as other protocol deviations identified based on data recorded on the eCRF and/or protocol deviation Logs from [REDACTED] Medical for all randomized patients.

Major protocol deviations defined as below will be listed separately:

- Lack of compliance defined as having administered <75% or >125% of the scheduled doses for the specified duration of the study
- Completion of the TOC/EOS Visit outside the specified visit window (Study Day 5 \pm 1 day) (if patient did not discontinue the study due to lack of treatment effect or worsening of the underlying condition requiring alternate or supplemental therapy).

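### Clinical cure has no condition on prohibited antidiarrheals or enteric-active antibiotics, so a self-treated completer can count as cured in the mITT assay-sensitivity analysis, and PP handling is left open

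*Protocol*

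**What the plan says.** **Endpoint.** Protocol 11.1.1 gives two routes to clinical cure. The first is "no stools or only formed stools within a 48 hour period and no fever, with or without other enteric symptoms, OR" and the second begins "no watery stools or no more than two soft stools passed within a 24 hour period with no fever", with symptoms limited to mild gas. The synopsis, 9.1.1, 13.2.3 and SAP 4.1 repeat both limbs. None adds a condition on other medication.

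**Prohibition.** Protocol 10.6 states "The following concomitant medications are prohibited from the signing of informed consent until the TOC/EOS Visit on Study Day 5". The list includes "antimicrobial agents with an expected activity against enteric bacterial pathogens" and "drugs effecting GI motility such as antimotility agents, adsorbent agents". Patients record what they take on the Supplemental Form, and SAP 8.4.3 has it entered in the eCRF. No section says what such use does to the endpoint.

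**Populations (13.2.2).** mITT requires eligibility, one dose and a Study Day 1 stool record. It has no criterion on later medication. PP removes patients with a major deviation bearing on the evaluation of treatment. It gives two examples, "lack of compliance defined as having administered <75% or >125% of the scheduled doses for the specified duration of the study" and a test-of-cure visit outside its window, says the list is not exhaustive, and leaves further items to the SAP. SAP 8.3 has the sentence "Major protocol deviations defined as below will be listed separately" and names the same two.

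**Discontinued patients (13.2.5).** Patients who worsen and need other therapy, and those who stop for lack of effect after three days of treatment, stay in PP with the last observation carried forward. Those who stop for other reasons are in mITT only.

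**The concern.** Patients are outpatients and travelers, with one scheduled call on Study Day 3. Protocol 7.1.3 itself names loperamide and several antibiotics as alternatives to rifaximin. A patient who is not improving may take one of these and still attend the test-of-cure visit. The first limb accepts 48 hours without stools even if other enteric symptoms continue, so an antimotility drug alone could satisfy it.

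For such a patient the endpoint reflects the other drug. Self-treatment is likeliest in patients whom study drug has not helped, so it would mostly turn failures into cures, and more of them in the arm with more failures. Differences between arms then shrink. Against placebo this costs assay sensitivity. Between the two rifaximin products, if it reached that analysis, it would make an inferior product look closer to the reference.

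**Working it through.** **1. The plan's own figures.** Randomized: 180/180/90. With 5% lost to mITT, 180 × 0.95 = 171 and 90 × 0.95 = 85.5 (stated 170 and 85). With a further 20% of mITT lost to PP, 171 × 0.80 = 136.8 (stated 135). The sample sizes reproduce. The planned cure rates and power are redacted and cannot be checked.

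**2. Inputs for the illustration.** Cure is 79% on Xifaxan (99/125) and 60% on placebo (78/129), from Study 1 in the label at Protocol Appendix I. The arm sizes are those of 13.1. The share f of true non-cures who self-treat, are not withdrawn and then meet the criteria is not in the documents. It is assumed equal in every arm and shown as a range.

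**3. Effect on the difference.** The observed rate is p + f(1 − p), so any true difference d becomes (1 − f)d.

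**4. Assay sensitivity, mITT, 170 vs 85, pooled two-sided Z test at 0.05.** Power = Φ[(d − 1.96·s0)/s1], where s0 is the pooled and s1 the unpooled standard error.

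| f | Active | Placebo | d | s0 | s1 | Power |
|---|---|---|---|---|---|---|
| 0 | 0.790 | 0.600 | 0.190 | 0.0592 | 0.0616 | 88.5% |
| 10% | 0.811 | 0.640 | 0.171 | 0.0572 | 0.0601 | 83.6% |
| 20% | 0.832 | 0.680 | 0.152 | 0.0549 | 0.0582 | 77.7% |

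For f = 0: (0.190 − 1.96 × 0.0592)/0.0616 = 1.20, and Φ(1.20) = 0.885.

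**5. Equivalence, only if these patients stay in PP as cures.** Take 135 per arm, margin 0.20 and a true difference exactly at the margin (59% vs 79%). The probability that the 90% interval lies inside the margin is 1 − Φ[(−0.20 + 1.645·s − d)/s], with s unpooled; the upper limit plays no part.

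- f = 0: d = −0.200, s = 0.0550, z = 1.645, probability 5.0%.
- f = 10%: 0.631 vs 0.811, d = −0.180, s = 0.0535, z = 1.27, probability 10.2%.

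**6. What the remedy could cost.** Suppose a share g in every arm takes such a drug regardless of response, and the drug does not change the outcome. Scoring all use as non-cure gives p(1 − g), so differences again shrink, to (1 − g)d. At g = 10% (assumed):

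- Sensitivity: 0.711 vs 0.540, s0 = 0.0632, s1 = 0.0643, (0.171 − 1.96 × 0.0632)/0.0643 = 0.73, power 76.8%.
- Equivalence at the margin: 0.531 vs 0.711, s = 0.0580, z = 1.30, probability 9.7%.

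**The case against.** **PP is not closed.** A reader might infer from the two listed deviations, repeated in SAP 8.3, that self-treated patients must enter the equivalence analysis as cures. The documents do not support that. Taking a prohibited drug that itself stops diarrhea fits the general PP exclusion readily, and Protocol 16.1 adds that deviations may make a patient non-evaluable. SAP 8.3 belongs to a safety-only plan that defines no PP population, so it cannot be read as completing the list. This objection stands. What remains is that prohibited medication is not named, and that excluding self-treated failures would remove failures selectively.

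**There are other safeguards.** Section 13.2.5 covers more than discontinuation for worsening. The Study Day 3 call and the test-of-cure visit both review medication, and 9.3.3 allows withdrawal for non-compliance. These narrow the gap to patients who are not withdrawn, but they do not say how those patients are scored. The secondary clinical-failure endpoint does not override cure, so the same patient could count as both.

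**The size is unknown.** No document gives a self-treatment rate, and f also requires that the drug works within the 24- or 48-hour window. This is correct; the figures are illustrations.

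**The endpoint follows regulatory guidance.** Protocol 9.2 says so. The guidance is not among the documents, and citing it does not supply the missing rule.

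Exclusion criterion 6b ("more than 2 doses of a symptomatic antidiarrheal compound such as antimotility agents, absorbent agents, and antisecretory agents") concerns the 8 hours before randomization and neither opens nor closes this gap.

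**Conclusion.** The gap is certain in mITT: as written, the plan scores a self-treated completer who meets the criteria as cured in the assay-sensitivity comparison. At the assumed f of 10% to 20%, that costs about 5 to 11 points of power (88.5% to 83.6% or 77.7%), given the label's cure rates and equal f across arms.

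For equivalence the finding is conditional. A doubling of the false-equivalence risk, from 5.0% to 10.2% at f = 10%, should not be read as a property of the plan. It needs these patients to be kept in PP as cures and a true difference exactly at the margin.

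Nor does this affect reported results. SAP section 9 removes all efficacy analyses because few patients were randomized. It is a flaw in the protocol's endpoint that would matter if the design were used again or efficacy were analyzed.

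**What to change.** **Endpoint (11.1.1, 13.2.3, synopsis; 9.1.1 to match).** State that a patient who, between first dose and the test-of-cure visit, takes a prohibited antidiarrheal or antimotility agent, or an antimicrobial active against enteric pathogens other than study drug or permitted antimalarial prophylaxis, is a non-cure in mITT.

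**PP (13.2.2, 13.2.5).** Name such use explicitly and fix its handling before unblinding. Primary: keep the patient in PP as a non-cure, in line with 13.2.5, which already keeps patients who need other therapy. Sensitivity analysis: exclude these patients.

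**Reporting.** Give the number of such patients per arm.

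**Cost.** One sentence in the definition, one PP rule, and one derivation from medication data already collected. Only recorded use can be scored. Cure rates fall in all arms, and use unrelated to response would itself dilute differences (10% use in every arm: power 76.8%, false equivalence 9.7%). The sensitivity analysis is therefore a necessary part of the fix. SAP 4.1 needs the change only if efficacy analyses are reinstated.

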11.1.2 Secondary efficacy endpoints

- TLUS defined as the interval beginning with the first dose of study drug and ending with the last unformed stool passed
- proportion of patients with clinical failure defined as failure to achieve formed stool within ≤ 3 days (72 hours) of the start of treatment with the study drug or clinical deterioration or worsening of symptoms by Study Day 5 (\pm 1 day)
- proportion of patients with improvement of diarrheal syndrome, defined as reduction of $\geq 50\%$ in the number of unformed stools (soft or watery) passed during the intervals 0-24 hours, 24-48 hours, 48-72 hours, 72-96 hours, and 96-120 hours after the first dose of study drug, compared to the number of unformed stools passed during the 24 hours immediately preceding first dose of study drug
- the number of unformed stools (soft or watery) passed during the intervals 0-24 hours, 24-48 hours, 48-72 hours, 72-96 hours, and 96-120 hours after the first dose of study drug
- the presence or absence and severity of signs and symptoms of enteric infection (abdominal pain/cramps, excessive gas/flatulence, nausea, vomiting, fecal urgency, tenesmus) – the proportion of patients with signs and symptoms of enteric infection during the intervals 0-24 hours, 24-48 hours, 48-72 hours, 72-96 hours, and 96-120 hours after the first dose of study drug
- microbiological cure defined as a post-treatment culture that was negative for the pre-treatment etiologic pathogen.

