7 INTRODUCTION

7.1 Background

7.1.1 Disease epidemiology

Travelers' diarrhea (TD) may be experienced by >60% of travelers from developed countries who visit developing countries, accounting for 40,000 travelers daily or > 15 million travelers annually¹. Travelers' diarrhea is usually contracted from contaminated food or water. Bacteria, in particular enterotoxigenic *Escherichia coli* (ETEC), are the most common cause of TD. Other bacteria implicated in travelers' diarrhea include enteroaggregative *E.coli* (EAEC), *Shigella*, *Salmonella*, and *Campylobacter*. Viruses (including Rotavirus) and protozoa (*Giardia lamblia*), make up the remainder of known causes^{2,3,4}.

The average duration of untreated travelers' diarrhea is approximately 4 days, with 50% of patients being free of symptoms within 48 hours^{5,6}. In a study of 1,455 Austrian tourists, abdominal cramps were reported in just over half of all patients, less than one third of patients reported nausea and/or vomiting and 13% of patients reported fever⁶. Travelers' diarrhea tends to have a longer duration in patients with other symptoms in addition to diarrhea (suggestive of severe travelers' diarrhea) and patients in whom pathogens are identified⁷.

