9.1.2.1 Screening and Randomization Visit (Study Day 0)

Screening procedures are as follows:

- ensure the patient is able to read and understand the Informed Consent Form (ICF) documents, and complete the Patient Diary and Supplemental Form
- obtain signed and dated informed consent
- check eligibility against study Inclusion and Exclusion Criteria (Sections 9.3.1 and 9.3.2, respectively)
- record medical and surgical history
- record demographic information (age, race, ethnicity and gender; country of residence; date of arrival in host country; previous country[s] visited between residence and host country)
- physical examination, including weight, height, and body mass index (BMI) (Section 12.2)
- vital signs (body temperature; respiratory rate, heart rate, blood pressure in the sitting position after 5 minutes rest; Section 12.3)
- clinical laboratory tests (hematology, chemistry, urinalysis; Section 12.4)
- signs/symptoms of TD (Section 11.2.1)
- baseline stool data (number and form of stools in the previous 24 hours; Section 11.2.2)
- stool sample (unformed) to be used for diagnosis and culture (Section 11.2.3); this stool sample may count as 1 of the 3 unformed stools that must be passed in the 24 hours prior to Randomization, as specified by the Inclusion Criteria
- urine pregnancy test for females of childbearing potential (not post-menopausal or who have not undergone surgical sterilization), only
- provide patients with Patient Diary to be completed during the study; patients will also receive instructions and practice in how to use Diary
- provide patients with the (paper) Supplemental Form to document the administration of any concomitant medications or occurrence of any AEs
- record prior medication taken within previous 4 weeks and occurrence of any AE (Section 12)
- dispense thermometer for patient use, with instructions for use
- documentation of any pre-treatment AEs

Once all Screening procedures are complete, eligible patients will be randomized to treatment (rifaximin, Xifaxan, or placebo) and receive assigned study treatment.

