9.3 Selection of Study Population

9.3.1 Inclusion Criteria

Patients eligible for enrolment in the study must meet all of the following criteria:

1. Patient is able to read and understand the language of the ICF and Patient Information
2. Patient has signed the ICF
3. Adult male or female aged ≥ 18 years
4. International travelers (e.g., visiting students/faculty or international tourists) with a duration of stay in host country long enough to attend scheduled visits.

5. Affected by naturally acquired acute diarrhea, defined as the passage of at least 3 unformed stools within the 24 hours immediately preceding randomization
6. At least one of the following signs and symptoms of enteric infection present at Screening:
 - a. abdominal pain or cramps
 - b. nausea
 - c. vomiting
 - d. fecal urgency
 - e. excessive gas/flatulence
 - f. tenesmus
7. Women of child-bearing potential (not post-menopausal or not surgically sterile) have a negative pregnancy test prior to beginning therapy and agree to use effective contraceptive methods during the study, as judged by the Investigator (including total abstinence from sexual intercourse)
8. Patient must have adequate general health as determined by the Investigator
9. Patient is willing and able (e.g., mental and physical condition) to participate in all aspects of the study, including providing an unformed stool sample at Screening and Randomization Visit, use of medication, completion of electronic Patient Dairy, attending scheduled visits, and compliance with protocol requirements as evidenced by providing signed written informed consent

NOTE: the unformed stool provided at the Screening/Randomization Visit may be counted as 1 of the 3 unformed stools specified in Inclusion Criteria 5.

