11.2 Efficacy Assessments

11.2.1 Symptoms

Symptoms of TD to be noted include the presence or absence and severity of enteric symptoms (abdominal pain/cramps, excessive gas/flatulence, nausea, vomiting, fecal urgency, tenesmus).

Patients will record the presence or absence and severity of any of these symptoms in the Patient Diary once daily, from the time of the Screening Visit until the TOC/EOS Visit on Study Day 5 (\pm 1 day).

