13.2.4.4 Unformed Stools

The number of unformed stools (soft or watery) passed during the intervals 0-24 hours, 24-48 hours, 48-72 hours, 72-96 hours, and 96-120 hours after the first dose of study drug will be compared between the three groups using repeated measures Poisson regression with treatment, time, and interaction as fixed effects, and with the baseline number of unformed stools as a covariate. In the event that the data are overdispersed, a negative binomial model will be used.

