13.2.4.5 Signs and Symptoms of Enteric Infection

The proportion of patients with the presence or absence and severity of signs and symptoms of enteric infection (abnormal pain/cramps, excessive gas/flatulence, nausea, vomiting, fecal urgency, tenesmus) during the intervals 0-24 hours, 24-48 hours, 48-72 hours, 72-96 hours, and 96-120 hours after the first dose of study drug will be compared between the three treatment groups with two-sided Z tests. The significance level of these tests will be set to 0.05.

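### The enteric-symptom comparison does not use the symptom status recorded at Screening: the planned Z test is valid, but stratifying by entry status would be more precise at almost no cost.

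*Protocol*

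**What the plan says.** Protocol 11.1.2 takes as the endpoint "the proportion of patients with signs and symptoms of enteric infection during the intervals 0-24 hours, 24-48 hours, 48-72 hours" and the two 24-hour intervals that follow, five in all, counted from the first dose. Under 13.2.4.5 these proportions "will be compared between the three treatment groups with two-sided Z tests", and "The significance level of these tests will be set to 0.05". Neither section mentions a baseline covariate, a stratum or a change from entry. Neither says whether the proportion is taken for each symptom or for any symptom.

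The entry information exists:

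- Inclusion criterion 6 in Protocol 9.3.1 requires "At least one of the following signs and symptoms of enteric infection present at Screening" and lists six.
- Protocol 9.1.2.1 makes signs and symptoms part of the Screening procedures.
- Protocol 11.2.1 has patients record presence and severity "once daily, from the time of the Screening Visit until the TOC/EOS Visit".
- SAP 8.4.1 summarises the six symptoms at baseline.

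The two stool endpoints measured over the same five intervals do use baseline. Improvement of diarrheal syndrome (13.2.4.3) is defined relative to the 24 hours before the first dose. The count model (13.2.4.4) is fitted "with the baseline number of unformed stools as a covariate".

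**The concern.** Criterion 6 asks for only one of six symptoms, so for a particular symptom some patients will not have it at entry. They can only show new onset. Patients who do have it can show persistence or resolution. The raw post-dose proportion adds the two together.

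If entry status predicts later status, two things follow. The unadjusted test carries outcome variation that a stratified test would remove, so it has less power. And in the one randomization that is realised, any chance difference between arms in who had the symptom at entry passes into the post-dose difference. At stake is how sharply, and how safely, a nominal result on one symptom can be read.

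**Working it through.** **Arm sizes.** Protocol 13.1 randomizes 180/180/90 and allows 5% exclusion from mITT: 180 × 0.95 = 171 and 90 × 0.95 = 85.5, against the stated 170 and 85. The synopsis and SAP section 5 allow a further 20% exclusion for PP: 171 × 0.80 = 136.8, against the stated 135. The plan's sizes reproduce. No power is stated for the symptom endpoint. The check below uses 171 (one active arm) versus 85 (placebo).

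**Assumed inputs, not in the documents.** The symptom persists into a later interval in 60% (placebo) or 40% (active) of those who had it at entry. New onset is 3, 5, 10 or 20% in the rest, equal in both arms. Entry prevalence *b* is 30, 50 or 90%. The only guide is the background tourist survey in Protocol 7.1.1: "abdominal cramps were reported in just over half of all patients, less than one third of patients reported nausea and/or vomiting". That is a different population, so it only suggests where to place the range.

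**Expected proportions.** Proportion = *b* × persistence + (1 − *b*) × onset.

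- *b* = 0.5, onset 3%: placebo 0.300 + 0.015 = 0.315; active 0.200 + 0.015 = 0.215; difference 0.10.
- *b* = 0.3, onset 3%: placebo 0.180 + 0.021 = 0.201; active 0.120 + 0.021 = 0.141; difference 0.06.

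**Hand check of unadjusted power** (*b* = 0.5, onset 3%). Pooled proportion = (171 × 0.215 + 85 × 0.315)/256 = 0.248. SE = √[0.248 × 0.752 × (1/171 + 1/85)] = 0.0573. z = 0.10/0.0573 = 1.74. Power ≈ Φ(1.74 − 1.96) = about 41%, which agrees with the table.

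**Chance imbalance.** SD = √[*b*(1 − *b*)(1/171 + 1/85)], which is 6.1 points at *b* = 0.3 and 6.6 points at *b* = 0.5. One SD of imbalance shifts the raw difference by SD × (persistence − onset). At *b* = 0.3 and onset 3% this is 0.061 × (0.60 − 0.03) = 3.5 points, beside a true difference of 6 points.

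**Simulation.** 200,000 trials per setting compare the pooled two-sided Z test with a Mantel-Haenszel test stratified by the entry symptom. The last two columns assume no drug effect (60% persistence in both arms) and count only trials whose imbalance exceeds 1 SD, which is roughly a third of trials.

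| *b* | Onset | Power, Z | Power, stratified | Gain (points) | Rejects if >1 SD, Z | Rejects if >1 SD, stratified |
|---|---|---|---|---|---|---|
| 30% | 3% | 24.0% | 30.9% | 6.9 | 12.1% | 5.1% |
| 30% | 5% | 23.0% | 27.8% | 4.8 | 11.2% | 5.1% |
| 30% | 10% | 20.6% | 22.7% | 2.1 | 9.6% | 4.9% |
| 30% | 20% | 17.8% | 18.1% | 0.3 | 7.7% | 5.0% |
| 50% | 3% | 41.5% | 52.6% | 11.1 | 11.0% | 5.1% |
| 50% | 5% | 40.7% | 49.9% | 9.2 | 10.5% | 5.0% |
| 50% | 10% | 39.0% | 44.8% | 5.7 | 9.3% | 4.9% |
| 50% | 20% | 36.2% | 38.2% | 2.0 | 7.7% | 5.0% |
| 90% | 3% | 78.6% | 81.7% | 3.2 | 7.0% | 5.0% |
| 90% | 20% | 78.5% | 79.6% | 1.1 | 6.0% | 5.0% |

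Over all randomizations both tests reject in about 5% of null trials in every row.

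**Second grid, different assumptions.** Here the effect was set so that the unadjusted test has about 80% power, with arms of 170 vs 85 and 170 vs 170, entry prevalence 30-70%, and later risk with versus without the entry symptom ranging from 40%/30% to 60%/10%. The gain is about 0 points when the entry symptom is weakly prognostic (R² about 0.01), 2-3 points when moderate (R² 0.09-0.12) and 4.5-8 points when strong (R² 0.18-0.28). Type I error of the Z test is 4.8-5.2% throughout.

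**The case against.** The strongest reply is that nothing here is invalid. Post-dose symptom burden, counting persistence and new onset together, is a legitimate quantity to compare between randomized arms. Unadjusted Z tests are also planned for clinical cure, clinical failure and microbiological cure (13.2.3, 13.2.4.2, 13.2.4.6), so this endpoint is not the only one without adjustment. All of that stands.

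A reader might infer that chance imbalance biases the comparison, or that the test rejects too often. The documents do not support that. Assignment is randomized, imbalance averages out, and the overall error rate is about 5% in every setting above. The 6-12% rates apply only after an unlucky split has been drawn.

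A reader might also take the 9 to 11 points as the expected loss. Those figures need 50% prevalence and 3-5% onset. At 10-20% onset the gain is between about 0 and 6 points. No section gives the prognostic strength of an entry symptom, and the survey in 7.1.1 has no figure for gas, urgency or tenesmus.

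Finally, the point needs a symptom-by-symptom reading. If any symptom is meant, criterion 6 puts entry presence at 100% in every arm and no imbalance in presence can arise. That limit also stands, and it is why the text should settle the reading.

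**Conclusion.** The point holds as a matter of efficiency. On a per-symptom reading, Protocol 13.2.4.5 leaves unused a baseline measurement that the trial already collects, although the stool-count analysis beside it adjusts for its own. The cost is about 0 to 11 points of power against placebo under the assumed 60% versus 40% persistence, largest when new onset is rare and about half the patients have the symptom at entry. The realised comparison is also more exposed to chance imbalance: with no drug effect and imbalance above 1 SD, about 6-12% of trials reject, against about 5% when stratified. In no setting checked did stratifying cost appreciable power or raise the error rate.

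The reach is limited. This is one secondary endpoint. Equivalence and assay sensitivity rest on clinical cure. SAP sections 1 and 9 drop all efficacy analyses because few patients were randomized, so the final analysis does not change. The point concerns the protocol's plan, and would matter if that plan were reused.

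**What to change.** In Protocol 13.2.4.5, state that:

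- each of the six symptoms is analysed separately in each interval;
- arms are compared by a Mantel-Haenszel risk difference, or a logistic model, stratified by presence of the same symptom at Screening;
- the raw proportions by arm are kept as descriptive results;
- the proportion resolved among patients who had the symptom at Screening is shown alongside. That group is defined before randomization, so the comparison within it remains a randomized one.

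The Mantel-Haenszel risk difference stays on the scale of the planned comparison. A logistic model would report a conditional odds ratio instead.

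The cost is a sentence or two of protocol text. It needs no new data, patients or procedures, and type I error stays at about 5%. SAP v1.0 contains no symptom efficacy analysis, so there is nothing in it to amend.
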